6.6 Randomisation

Not applicable. Single-arm feasibility study.

6.7 Blinding

Not applicable. Single-arm feasibility study.

6.8 Baseline Assessments

Baseline assessment will include:

1. Detailed collection of medical history which should include atrial fibrillation history, previous cardiac procedure (cardiac surgery, atrial fibrillation ablation, direct current cardioversion), significant co-morbidities.
2. Imaging data recorded previously as part of standard clinical practice: left ventricular systolic function, diastolic function, evidence of valvular heart disease, cardiac chamber size.
3. Current medications
4. Height, weight, and BMI

6.9 Intervention – LINQ II ICM implant

The LINQ II™ ICM will be implanted as a Day Case. The procedure will be performed under sterile conditions, will require local anaesthetic (lidocaine 1%), and insertion tools supplied by the manufacturer will be used. If there is suboptimal R-wave amplitude the operator can reposition the device. The operator may choose to close the wound with steri-strips, surgical glue or a suture. LINQ II™ ICM implant procedure is safe and minimally invasive and takes <15 minutes to do. There are no

known contraindications. Potential adverse events occur in less than 1% of procedures and include bruising, haematoma, superficial infection, keloid scar formation, migration or extrusion.

The LINQ II™ ICM is in constant communication with the smartphone app through low-energy Bluetooth and transmits stored episodes to Medtronic servers via its smartphone app. Participants will be instructed to always keep the Bluetooth “on” and to permit a pop-up notification to appear on their smartphone if the LINQ II™ ICM loses connection with the smartphone app. ICM recordings can only be accessed on Medtronic servers through the clinician web portal (Medtronic CareLink™ Network). The assigned study ID number will be used to register the device in the CareLink™ Network; thus, no identifiable patient information will be in the servers. Access to these servers is via the clinician web portal and it is password-protected. Transmission reports will be downloaded from the Medtronic™ servers and stored in a password protected folder that will only be used in OUH trust computers for adjudication at the end of study. This system is part of routine clinical practice around the UK in according with GDPR guidelines.

For this trial, if the LINQ II™ ICM detects an AF episode or AF burden that meet criteria for OAC initiation it will transmit in real-time to CareLink™. Our messaging software will then generate an email to the research team and a text message to the participant’s smartphone. The sender info of the text message will include the RESPOND-AF research team telephone number and prompts patients to initiate OAC. Participants will be instructed to acknowledge receipt of the notification by replying to the text message once they have taken their OAC, and thus record a time stamp (figure 4). Adjudication of all alerts as either appropriate or inappropriate by members of the research team and participants contact will take place within 48 hours.

[figure not shown]

Figure 6. Summary of study procedures during treatment period.

[figure not shown]

Figure 7. Algorithm to improve compliance with LINQ II ICM and ensure daily transmission of monitoring data.

6.10 Subsequent Visits

Visit 1 (Eligibility assessment, LINQII ICM Implant and Run-in period): If a participant agrees to take part, he/she will be evaluated against the entry criteria and exclusion criteria. Other tests, such as echocardiography, may be organised. If eligible, the participant will be asked to sign an informed consent.

Participants will have a LINQ II ICM implant. They will be taught how to pair the LINQ II ICM to their smartphone and how to use the smartphone app (MyCareLink) to record and send manual transmissions. Participants will be given a 3-month supply of a DOAC and instructed to continue OAC for 30 days (run-in period). At the end of the run-in period, they will enter the treatment period and will be contacted by the research team to either continue on OAC (if they have not met the discontinuation criteria) or to discontinue their OAC and commence the "as-required" regimen guided by smartphone alerts.

The investigator may consider the initiation or optimisation of anti-arrhythmic drugs at this time.

Visit 2 (End of study): At the end of study, patients will attend Device Clinic for a final clinical review. At this time, they may choose to have the ICM removed. An updated medical and drug history will be recorded. At this point, patients will be instructed to revert to standard clinical care.

Unscheduled visits: In addition to the protocol-specified visits, patients may be seen at any time throughout the study at the discretion of the investigator. This may include and it is not limited to visits to review medication, LINQII ICM troubleshooting, review adverse events, perform direct current cardioversion or other procedures such as catheter ablations. Periprocedural OAC will follow current ESC guidelines recommendation.

6.11 Early Discontinuation/Withdrawal of Participants

During the trial a participant may choose to withdraw early from the trial treatment at any time. This may happen for several reasons, including but not limited to:

- The occurrence of what the participant perceives as an intolerable AE.
- Inability to comply with trial procedures.
- Participant decision.
- Loss to follow-up.

Participants may choose to withdraw from study assessments but remain on study follow-up.

Participants may also withdraw their consent, meaning that they wish to withdraw from the study completely.

In addition, the Investigator may discontinue a participant from the trial treatment at any time if the Investigator considers it necessary for any reason including, but not limited to:

- Pregnancy.
- Ineligibility (either arising during the trial or retrospectively having been overlooked at screening).
- Significant protocol deviation.
- Significant non-compliance with treatment regimen or trial requirements.
- Disease progression which requires discontinuation of the trial medication or results in inability to continue to comply with trial procedures.

The type of withdrawal and reason for withdrawal will be recorded in the CRF.

In case of withdrawal from the study in an early stage (before intervention), the patient data will be excluded from the analysis and a new participant will be enrolled.

If the participant is withdrawn due to an adverse event, the Investigator will arrange for follow-up visits follow-up visits or telephone calls until the adverse event has resolved or stabilised.

If the participant withdraws, he/she may choose to:

- Continue to have the routine LINQ II ICM downloads as per clinical need.
- To have the LINQ II ICM turned off.
- To have the LINQ II ICM removed. The investigators will organise an outpatient procedure.

6.12 Definition of end of study

The end of the follow-up period will be when all participants have had a minimum of 12 months in the treatment period. The end of the study period will be 4 months after the end of follow-up. During this time investigator will conduct the analysis and draft a report of the findings.

9 TRIAL INTERVENTIONS

9.1 Other Interventions

The decision to organise a direct current cardioversion and/or optimisation of any antiarrhythmic medications is common in the management of AF and will be left to the Investigators discretion. Investigator may also decide to offer participants a catheter ablation if deemed appropriate. Periprocedural OAC will follow current ESC guidelines recommendation.

10 SAFETY REPORTING

10.1 Definition of Serious Adverse Events

A serious adverse event is any untoward medical occurrence that:

- results in death.
- is life-threatening.
- requires inpatient hospitalisation or prolongation of existing hospitalisation.
- results in persistent or significant disability/incapacity.
- consists of a congenital anomaly or birth defect.

Other 'important medical events' may also be considered a serious adverse event when, based upon appropriate medical judgement, the event may jeopardise the participant and may require medical or surgical intervention to prevent one of the outcomes listed above.

NOTE: The term "life-threatening" in the definition of "serious" refers to an event in which the participant was at risk of death at the time of the event; it does not refer to an event which hypothetically might have caused death if it were more severe.

10.2 Reporting Procedures for Serious Adverse Events

A serious adverse event (SAE) occurring to a participant should be reported to the REC that gave a favourable opinion of the study where in the opinion of the Chief Investigator the event was 'related' (resulted from administration of any of the research procedures) and 'unexpected' in relation to those procedures. Reports of related and unexpected SAEs should be submitted within 15 working days of the Chief Investigator becoming aware of the event, using the HRA report of serious adverse event.

10.3 Adverse Events

Adverse events (AE) will be collected upon enrolment to the study until and including the final visit. All adverse events will be recorded in the CRF and should include the following:

- AE.
- Date of AE.

- Date when investigator become aware of AE.
- Date of hospitalisation.
- Date of discharge.
- Outcome.
- Whether this event constitutes a serious adverse event (SAE).
- Whether this event is a clinical endpoint.
- Action taken.

All potential neurological symptoms or events will be formally assessed by stroke physicians or neurologists.

Clinical endpoint definitions are according to the outcome measures in AF endorsed by the Heart Rhythm Society.⁽³¹⁾

- **Stroke:** defined as acute episode of focal or global neurological dysfunction caused by brain, spinal cord, or retinal vascular injury as a result of haemorrhage or infarction. Symptoms or signs must persist for more than 24 hours, or if documented by CT, MRI or autopsy, the duration of symptoms/signs may be less than 24 hours. Stroke may be classified as ischemic (including haemorrhagic transformation of ischemic stroke), haemorrhagic, or undetermined.
- **Systemic embolism:** defined as an acute arterial insufficiency or occlusion of the extremities or any non-central nervous system (CNS) organ associated with clinical, imaging, surgical/autopsy evidence of arterial occlusion in the absence of other likely mechanism.
- **Major bleeding:** Fatal bleeding AND/OR symptomatic bleeding in a critical area or organ, such as intracranial, intraspinal, intraocular, retroperitoneal, intraarticular, pericardial, or intramuscular with compartment syndrome AND/OR bleeding causing a fall in haemoglobin level of 2 g/dL (1.24 mmol/L) or more, or leading to transfusion of two or more units of blood.
- **Minor bleeding:** All nonmajor bleeds. Minor bleeds are further divided into clinically relevant and not.

11 STATISTICS AND ANALYSIS

11.1 Analysis of Outcome measures

Descriptive statistics will be reported as count (percentage) for the categorical variables and mean (\pm standard deviation) for the continuous variables. The primary endpoint will be total OAC utilisation, which will be calculated by dividing the total number of days on OAC with the total follow-up duration. Adjudication of all LINQ II™ ICM electrograms will be performed by the research team to determine if notification was appropriate or inappropriate. The percentage of appropriate notifications and the mean time (\pm standard deviation) from notification to taking OAC will be measured. The associations of the measurements with the patient demography, medical history, imaging biomarkers, medications, etc. will be investigated.

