3.3 Public and patient involvement

Patient-public involvement: We conducted a survey in 320 patients with a diagnosis of AF in collaboration with the AF association. In this survey, a quarter of patients forget to take their OAC at least once a week, one third has experienced side effects from taking OAC and 70% worry about bleeding complications. Importantly, it highlights that patients would welcome alternative stroke prevention strategies, and more than half (55%) would choose an as-required OAC guided by an ICM if this strategy was deemed safe.

An ICM implant does not appear to be a barrier to recruitment in trials using as-required OAC. In a short survey of patients with a Reveal LINQ at the John Radcliffe Hospital, 92% were very satisfied and would have a Reveal LINQ purely as a research device.

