4. OBJECTIVES AND OUTCOME MEASURES

Objectives	Outcome Measures	Timepoint(s) of evaluation of this outcome measure (if applicable)

Primary Objective To investigate the reduction in oral anticoagulation (OAC) utilisation during follow-up.
	
Primary Outcome Measures Calculate the proportion of time off anticoagulation OAC
	
During follow-up (minimum 13 months)

Secondary Objectives
 
 1. Thromboembolic events (Ischaemic stroke, transient ischaemic attack (TIA) and systemic embolism) 2. Major bleeding 3. Minor bleeding 4. Any stroke (ischaemic, haemorrhagic or undetermined). 5. All-cause mortality 6. Protocol adherence 7. To assess response time from AF episode onset to patient starting as-required OAC 	
Secondary Outcome Measures
 
 1. Calculate the rate of ischaemic stroke, TIA and systemic embolism in patients on as-required OAC 2. Calculate the rate of major bleeding in patients on as-required OAC 3. Calculate the rate of minor bleeding in patients on as-required OAC 4. Calculate the stroke rate (ischaemic, haemorrhagic or undetermined) 5. Calculate the rate of all-cause mortality in patients on as-required OAC 6. Calculate the number of daily transmissions and percentage of patients that restarts OAC within 24 hours of the smartphone-alert. 7. Time from AF episode onset to detection, time to alerts being sent and acknowledged and OAC 	
 1. During follow-up (minimum 13 months) 2. During follow-up (minimum 13 months) 3. During follow-up (minimum 13 months) 4. During follow-up (minimum 13 months) 5. During follow-up (minimum 13 months) 6. During follow-up (minimum 13 months) 7. During follow-up (minimum 13 months)

	being taken by the participant. Proportion of missed AF episodes, transmissions or alerts.	
--	--	--

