5. STUDY DESIGN

The objective of the RESPOND-AF study is to evaluate the feasibility of delivering “as-required” oral anticoagulation (OAC) guided by continuous rhythm monitoring with an implantable cardiac monitor (LINQ II™ ICM) and automated patient smartphone alerts, and to assess if this approach reduces OAC utilisation.

This study will recruit 50 participants with current paroxysmal or persistent AF being treated with a rhythm control strategy and infrequent AF episodes. The study consists of two main phases: (1) the active run-in period, which lasts one month, and (2) the treatment period which will last a minimum of 12 months.

All potentially eligible participants will undergo an enrolment visit (Visit 1) and, if they fulfil all the eligibility requirements, they will enter the active run-in period and will have a LINQ II™ ICM implant as a Day Case Procedure. A 3-month supply of their previously prescribed oral anticoagulant will be issued.

During the run-in period, participants will continue to take OAC for 30 days. Day 30 will be the start of the treatment period and the participant will be contacted by the research team. If participants meet the discontinuation criteria, they will be asked to stop OAC, otherwise they will remain on OAC until discontinuation criteria (freedom from AF episodes longer than 1 hour and/or daily burden of more than 1 hour for 30 consecutive days) are met. The purpose of the run-in period is to ensure that patients do not discontinue their pre-study OAC prematurely, i.e., less than 30 days after their last significant AF episode.

[figure not shown]

Figure 3. Study flow chart

In the treatment period patients will only be taking daily OAC if there has been an AF episode in the previous 30 days. If the LINQ II™ ICM detects an episode of AF meeting the initiation of OAC criteria,

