At the end of the study, participants will be invited to attend the Device Clinic for a final manual device interrogation and full clinical review of their medical care over the previous 12 months (Visit 2). They may choose to have the LINQ II™ ICM explanted during the final visit or leave it in-situ. It can be deactivated or else continue to monitor the patient’s heart rhythm. The primary endpoint is total OAC utilisation which will be calculated by dividing the number of days on OAC by the total number of days during the treatment period.

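### The primary endpoint, total OAC utilisation, has two denominators: treatment-period days in Section 5 and total follow-up in Section 11.1

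*Protocol*

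**What the plan says.** Section 5 (Study Design) names total OAC utilisation as the primary endpoint and says it will be "calculated by dividing the number of days on OAC by the total number of days during the treatment period". Section 11.1 names the same endpoint and says it will be "calculated by dividing the total number of days on OAC with the total follow-up duration". The Synopsis and the Section 4 table express the primary outcome as its complement, the proportion of time off OAC, with the timepoint "During follow-up (minimum 13 months".

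Section 5 also sets out the phases: "1) the active run-in period, which lasts one month, and (2) the treatment period which will last a minimum of 12 months". On the run-in it says "During the run-in period, participants will continue to take OAC for 30 days", and it fixes the boundary between the phases: "Day 30 will be the start of the treatment period". Section 6.12 ends follow-up once every participant has had at least 12 months in the treatment period. It does not say when follow-up begins.

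**The concern.** The two definitions agree only if follow-up and treatment period mean the same interval, and the protocol's own durations indicate that they do not. If follow-up includes the run-in, Section 11.1 counts 30 days on which OAC is required of everyone. Those days carry no information about what the as-required strategy saves, and they pull measured time off OAC downwards.

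The study is single-arm and descriptive, so no hypothesis test, success threshold or sample size is affected. But this one estimate is the primary result, and two analysts working from different sections would report different values. Leaving the choice open until the data are in also allows the more favourable figure to be picked.

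**Working it through.** **Inputs**
- Run-in R = 30 days, OAC to be taken throughout (Section 5).
- Treatment period at least 12 months (Section 5); taken as T = 365 days (assumption).
- Minimum follow-up 13 months (Synopsis, Section 4).
- Illustrative reductions in OAC time of 86.5% (paroxysmal) and 46.3% (recurrent persistent), from the retrospective device cohort in Section 3. These come from a different population and are not planning assumptions. They correspond to treatment-period utilisation U = 0.135 and 0.537.

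**Which window is total follow-up?** 1 month + 12 months = 13 months. The stated minimum is reproduced exactly when the run-in is counted; the treatment period alone gives 12.

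**Formulas.** Let a be the share of run-in days on which OAC is taken.
- Section 5: utilisation = U.
- Section 11.1: utilisation = (30a + U·T)/(T + 30).
- Gap = 30(a − U)/(T + 30).
- With a = 1, time off under Section 11.1 = T/(T + 30) times time off under Section 5, for every U.

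**Minimum follow-up, a = 1, T = 365**
- Ratio of time off: 365/395 = 0.924.
- U = 0 (OAC never taken after Day 30): 30/395 = 7.6% utilisation instead of 0%, so time off cannot exceed 92.4%.
- U = 0.135: gap 30(0.865)/395 = 6.6 points; time off 86.5% becomes 79.9%.
- U = 0.537: gap 30(0.463)/395 = 3.5 points; time off 46.3% becomes 42.8%.

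**Longer follow-up.** Section 5.1 allows 20 months for recruitment and follow-up together. Taking off 13 months leaves about 7 for recruitment. If recruitment is uniform and follow-up ends on a common date (assumptions), the mean treatment period is 12 + 3.5 = 15.5 months, about 472 days. The earliest recruits could reach 20 − 1 = 19 months, about 580 days.

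| T (days) | Gap at U = 0 | Gap at U = 0.135 | Gap at U = 0.537 |
|---|---|---|---|
| 365 | 7.6 | 6.6 | 3.5 |
| 472 | 6.0 | 5.2 | 2.8 |
| 580 | 4.9 | 4.3 | 2.3 |

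Gaps are in percentage points, a = 1.

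**Imperfect run-in adherence, T = 365.** The survey in Section 3.3 reports that "a quarter of patients forget to take their OAC at least once a week". If a quarter of participants miss one day in seven, a = 1 − 0.25/7 = 0.964 and the gaps are 7.3, 6.3 and 3.2 points. If everyone does, a = 6/7 = 0.857 and the gaps are 6.5, 5.5 and 2.4 points.

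**Mixing the two sections.** Section 11.1 takes all days on OAC as numerator. Placed over treatment-period days alone, this would give a participant always on OAC 395/365 = 108.2%. Numerator and denominator must share one window.

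**The case against.** Section 11.1 never mentions the run-in, and total follow-up duration is undefined. Section 6.12 closes follow-up by reference to the treatment period, and Section 5 describes the final visit as reviewing the preceding 12 months. Section 11.1 could therefore be loose shorthand for the explicit Section 5 definition. The 13-month label may also be generic: it is attached to every outcome, including some, such as restarting OAC after an alert, that apply only once the as-required regimen has begun. The safety window in Section 10.3 ("Adverse events (AE) will be collected upon enrolment to the study until and including the final visit") says little about an OAC denominator.

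These points are fair, and they are why including the run-in remains an inference. They do not remove the mismatch. No text equates the two intervals, and if follow-up did mean the treatment period, the 13-month minimum attached to the primary outcome would itself be wrong.

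Two further points stand. The largest gaps belong to the minimum follow-up; at a plausible average they are nearer 3 to 5 points on the illustrative figures, which does not change the qualitative reading of reductions of 46% or 87%. Nor is dilution inevitable: if a participant's treatment-period use exceeds run-in use, the sign reverses. For example, a = 6/7 and U = 0.95 give 30(0.857 − 0.95)/395 = −0.7 points. With OAC taken as instructed in the run-in, this cannot happen.

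A whole-follow-up estimate is also a legitimate description. The protocol simply has to choose.

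**Conclusion.** The concern holds. The current text gives the sole primary endpoint two different denominators and does not reconcile them. That contradiction is certain. That total follow-up includes the run-in is an inference, well supported by the 13-month minimum.

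On that reading, with full run-in adherence and a 365-day treatment period, the choice of section moves the primary result by up to 7.6 percentage points, and by 6.6 and 3.5 points on the illustrative figures. Under Section 11.1 the result also depends on how long each participant is followed, because the fixed 30 days weigh less in longer follow-up. The effect is moderate and changes no inferential decision, but it should be settled before analysis.

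**What to change.** Define one window and apply it to both numerator and denominator. Preferred: OAC utilisation = days on OAC in the treatment period ÷ days in the treatment period, from Day 30 to the end of follow-up, with time off OAC as 1 minus this. The reason is that the strategy cannot act before Day 30. Align Section 11.1 and the primary-outcome timepoint in the Synopsis and Section 4 with Section 5, and label any figure that includes the run-in as supplementary.

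If the sponsor prefers the whole of follow-up, change Section 5 instead and state when follow-up starts.

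The cost is protocol wording only. No new data are needed, and both versions can be calculated from the same records.

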	
attacks (TIA) and systemic embolism)
 
2. Major bleeding
 
3. Minor bleeding
 
4. Any stroke (ischaemic, haemorrhagic or undermined)
 
5. All-cause mortality
 
6. Protocol adherence
 
7. To assess response time from AF episode onset to patient starting as-required OAC
	
patients on as-required OAC
 
2. Calculate the rate of major bleeding in patients on as-required OAC
 
3. Calculate the rate of minor bleeding in patients on as-required OAC
 
4. Calculate the stroke rate (ischaemic, haemorrhagic or undetermined)
 
5. Calculate the rate of all-cause mortality in patients on as-required OAC
 
6. Calculate the percentage of daily automatic transmissions and percentage of patients that restart OAC within 24 hours of the smartphone-alert.
 
7. Time from AF episode onset to detection, time to alerts being sent and acknowledged and OAC being taken by the participant. Proportion of missed AF episodes, transmissions or alerts.
	
2. During follow-up (minimum 13 months)
 
3. During follow-up (minimum 13 months)
 
4. During follow-up (minimum 13 months)
 
5. During follow-up (minimum 13 months)
 
6. During follow-up (minimum 13 months)
 
7. During follow-up (minimum 13 months)

Intervention(s)	
As-required oral anticoagulation (OAC):
 
 • Initiate OAC if continuous AF episodes longer than 1 hour or total AF burden of more than 60 minutes (>4.2%) over a 24-hour period. 
 ○ Dabigatran ○ Rivaroxaban ○ Apixaban 		

	
○ Edoxaban• Discontinue OAC if freedom over a consecutive 30-day period from: (1) AF episodes longer than 1 hour, and (2) AF burden more than 60 minutes in any 24-hour period.
--	--

CONFIDENTIAL

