3.1 SMART-ALERT study

SMART-ALERT study: (*study complete, analysis and preparation of manuscript ongoing*) In this study our research group aimed to assess the feasibility and robustness of: (1) the closed-loop system

using LINQ II™ ICM remote monitoring to detect AF, (2) our custom software platform (discussed in section below) to alert patients of the AF episode, (3) of patients acknowledging receipt of the alert.

We also assessed the accuracy of wearable devices during the follow-up period: the Apple Watch and the SkyLabs CART-I Smart Ring. We used the LINQ II as the gold standard comparator of their accuracy.

Preliminary results: We recruited 50 patients with known frequent episodes of AF. Early results indicate this approach is reliable and accurate. On interim analysis, the median time from AF episode detection to SMS alert was 183 minutes (3.1 hours). The median time from SMS alert to patient reply was 5.1 minutes. Only 1 episode took longer than 24 hours for the patient to reply. On 3 occasions there was no patient reply. The median total time from AF episode detection to patient reply was 296.5 minutes (4.9 hours) and 94% of replies occurred within 24 hours.

In the context of the RESPOND-AF study, a median time of 4.9 hours from AF episode detection to commencing oral anticoagulation would be deemed safe and appropriate. In fact, most of the patient responses in SMART-ALERT occurred within 1 - 3 hours.

These timings represent the combined results from versions 1.0, 2.0 and 3.0 of our custom software programme. The earlier versions had intermittent technical issues, with periods of the software programme crashing and not automatically restarting. On these occasions manual restart of the software programme was required. This resulted in occasions with delays to SMS alerts being sent to patients while versions 1.0 and 2.0 of the software programme were running. Version 3.0 did not require any manual restart while operational, correcting the previous technical issues.

We are undertaking further analysis of the performance of each version of the software programme. We expect that the detection and response times will be much improved for version 3.0 of the software programme.

[figure not shown]

Figure 2. Preliminary results of interim analysis A) Time to AF episodes to SMS alert, B) time from SMS alert to acknowledgment, total time

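### Section 11.1 fixes mean ± SD for time from notification to taking OAC and, by its general rule, for the other response times, although the pilot figures indicate asymmetry and are reported as medians

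*Protocol*

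**What the plan says.** Section 11.1 sets a general rule: "Descriptive statistics will be reported as count (percentage) for the categorical variables and mean" with standard deviation for the continuous ones. It then singles out one response time: "The percentage of appropriate notifications and the mean time", again with standard deviation, from notification to taking OAC. No median, quartile or range is offered.

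Secondary outcome 7 (Synopsis and Section 4) lists further intervals: "Time from AF episode onset to detection, time to alerts being sent and acknowledged and OAC being taken by the participant". It names no summary for them, so the general rule in 11.1 governs.

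Section 3.1 describes the pilot of the same alert system and uses medians throughout. Detection to SMS alert had a median of 183 min. For the next step, "The median time from SMS alert to patient reply was 5.1 minutes". For the whole path, "The median total time from AF episode detection to patient reply was 296.5 minutes (4.9 hours) and 94% of replies occurred within 24 hours". On late and missing replies it says "Only 1 episode took longer than 24 hours for the patient to reply" and "On 3 occasions there was no patient reply". The same section describes a median of 4.9 h from detection to starting OAC as acceptable for RESPOND-AF. It also warns: "These timings represent the combined results from versions 1.0, 2.0 and 3.0 of our custom software programme".

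**The concern.** Response times cannot be negative and usually have a long right tail. For such data the mean lies above what most participants do, and the SD can exceed the mean, so that mean minus SD is a negative time. The trial is meant to show whether alert-triggered OAC is feasible, and speed of response is a named secondary objective. If a few late responses dominate the one response-time summary that 11.1 names, it tells the reader little about the typical response. It would also be on a different footing from the pilot medians and from the median that Section 3.1 calls acceptable.

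**Working it through.** **Inputs, all from Section 3.1.** Detection to reply: median 296.5 min, 94% of replies within 24 h (1,440 min), hence 6% later. Alert to reply: median 5.1 min, one reply later than 24 h. Patients: 50. The number of replies is not given.

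**Unit check.** 183/60 = 3.05 h (stated 3.1) and 296.5/60 = 4.94 h (stated 4.9). Both agree.

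**Step 1: can detection to reply be symmetric?** A symmetric, non-negative time with median m cannot exceed 2m. Here 2 × 296.5 = 593 min. The pilot has 6% of replies beyond 1,440 min, so symmetry is ruled out without fitting any curve. As a cross-check, a normal curve centred at 296.5 min with 94% below 1,440 min needs SD = (1,440 − 296.5)/1.555 = 735 min. It would put about 34% of times below zero.

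**Step 2: floor on the mean of alert to reply.** The sentence on the single late reply follows the 5.1 min median, so I read it as timed from the alert. The smallest possible mean has half the replies at 0, the rest at 5.1 min and one at 1,440 min:

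mean ≥ 5.1/2 + (1,440 − 5.1)/n = 2.55 + 1,434.9/n

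| Assumed n | Floor on mean (min) |
|---|---|
| 50 | 31.2 |
| 100 | 16.9 |
| 200 | 9.7 |
| 400 | 6.1 |

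The floor exceeds the median of 5.1 while n < 1,434.9/2.55 = 562.7, or 562.7/50 = 11.3 replies per pilot patient.

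**Step 3: how far does one late reply move the mean?** This depends on the spread of the others.
- All others at 5.1 min: the mean is 5.1 + 1,434.9/n, that is 33.8, 19.4 and 12.3 min for n = 50, 100 and 200. These are 6.6, 3.8 and 2.4 times the value without the late reply. The SD is 1,434.9/√n = 203, 143 and 101 min, far above the mean.
- Others widely spread (lognormal, median 5.1, sigma 2, capped at 1,440 min, by simulation): the factors are only 1.8, 1.4 and 1.2.

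**Step 4: what the pilot does not settle.** Without a shape assumption, the detection-to-reply figures give only mean ≥ 0.44 × 296.5 + 0.06 × 1,440 = 217 min. That is below the median. The asymmetry is established; the size of the gap between mean and median is not.

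**The case against.** The strongest case against is that the pilot does not carry over, and much of it stands. The pilot results are interim and pooled. Section 3.1 attributes some delays to crashes of versions 1.0 and 2.0 that held up the sending of alerts, and says that version 3.0 corrected them. Those delays fall before notification, so they do not belong to the interval that 11.1 names. They do not, however, explain a reply more than 24 h after an alert. Section 3.1 also places most patient responses within 1 to 3 hours without naming the clock, which is hard to square with either median.

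A reader might infer that the mean of alert to reply must exceed its median. It need not. The reply count is unstated, and the pilot enrolled patients with frequent AF. One patient described in Section 3.1 had 11 episodes in six months, close to the 11.3 per patient at which the bound stops working.

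A reader might also infer that unanswered alerts drop out of the mean and bias it. The documents do not support that. Section 11.1 times the taking of OAC. Section 5 provides a second notification and then direct staff contact for silent participants, at which a start time can be obtained. A median of observed replies would omit the same alerts, so this is no argument for a median over a mean.

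Nor is comparison with the pilot impossible. The same group holds the pilot data and can compute either summary. The 4.9 h remark is background, not a success criterion.

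Finally, naming a mean does not forbid a median, a mean does respond to late starts, and outcomes 6 and 7 already cover a 24 h percentage and missed alerts. This is why the mean should stay as a supplement. But outcome 6 counts patients and runs from the alert, whereas the 24 h and 48 h target in Section 3 runs from AF onset. Because the protocol itself names mean ± SD, the choice is not simply left to a later plan.

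**Conclusion.** The concern holds as a minor point. Mean ± SD is a poor sole summary for times that the protocol's own pilot shows to be asymmetric from detection to reply, and probably asymmetric from alert to reply. It is likely to be driven by a few late responses and to misdescribe the typical one.

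The size of the effect in RESPOND-AF is not known. It is tempting to say that the mean from detection would be about 8 h. A lognormal curve through the pilot points has sigma = ln(1,440/296.5)/1.555 = 1.016, mean = 296.5 × exp(1.016²/2) = 497 min (8.3 h) and SD 669 min. That figure rests on a chosen curve. It also concerns an interval that 11.1 does not name, includes delays from the earlier software and ends at acknowledgement rather than intake. It illustrates the issue and does not predict the result.

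The verdict assumes that the 94% is timed from detection and the single late reply from the alert. If that reply was also timed from detection, Step 2 falls and Step 1 stands. The primary endpoint, any test and the sample size are unaffected.

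**What to change.** Two sentences in Section 11.1 are enough:

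- Report each response interval, with its start and end stated (notification to OAC, detection to OAC, AF onset to OAC), as median with IQR and range, keeping mean ± SD as a supplement.
- Report the proportion of appropriate alerts with OAC started within 24 h and within 48 h of AF onset, the limits that Section 3 already sets. Where there is no reply, use the start time obtained at the staff contact described in Section 5. Keep alerts without a known start time in the denominator.

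Cite the pilot medians of 5.1 min and 4.9 h only as approximate context, because they timed acknowledgement.

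The cost is a little extra descriptive analysis. Outcome 7 already calls for onset, detection, alert, acknowledgement and OAC times, and the staff contacts are already planned. The OAC-utilisation summary need not change.
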